4.3 Efficacy Measurements

Adverse events will be monitored throughout the trial and graded in severity according to the guidelines outlined in the NCI Common Terminology Criteria for Adverse Events (CTCAE) version 5.0

Patients will be evaluated every 8 weeks (\pm 7 days) with radiographic imaging to assess response to treatment. CT or MRI will be used, per PI discretion, to scan areas of known disease. All imaging will be assessed using Response Evaluation Criteria in Solid Tumors (RECIST) 1.1 for determination of overall response rate (ORR) and progression-free survival (PFS).

4.4 Inclusion Criteria:

1. Histologically proven salivary gland carcinoma (WHO, 2005) arising from a previous head and neck primary site, and located within the head and neck region, lung or bone, and who are not candidates for curative intent therapy.
2. ≥ 18 years old at the time of signing informed consent.
3. Demonstrated disease progression during, or after discontinuation, of the most recent line of systemic therapy.
4. Have received any number lines of prior systemic therapy (including systemic therapy in the curative intent setting).
5. Have a target lesion/s deemed suitable by the treating physicians for SBRT with the intent of palliation or prevention of symptoms. This lesion must be:
 - a) 1-3 non-overlapping sites in the head and neck region OR
 - b) metastatic lesions outside the H&N region in the lung or bone (a minimum of 1 and a maximum 5 lesions will be irradiated), provided there is no significant overlap between the lesions.

Patients should have RECIST 1.1 criteria measurable disease in addition to the lesion/s treated with SBRT. If the site/s of SBRT were previously radiated to high dose RT (>50 Gy), there should be >6 month time interval between the last dose of radiation and the start of SBRT.

6. Have the ability to tolerate required SBRT-related procedures (e.g.: lie flat and hold position for treatment) as determined by the treating physician
7. Be willing and able to provide written informed consent for the trial and comply with the study visit requirements
8. Have measurable disease based on RECIST 1.1. (in addition to the lesion/s that will be treated with stereotactic radiation therapy)

9. Have provided tissue from an archival tissue sample or newly obtained core or excisional biopsy of a tumor lesion. Tissue requirement will be waived if deemed contraindicated or not clinically available/accessible for resection per the treating physician (PI approval required).
10. Have a performance status of 0 or 1 on the ECOG Performance Scale.
11. Demonstrate adequate organ function as defined in below, based on screening labs should be performed within 10 days of treatment initiation.
 - Hemoglobin ≥ 9.0 g/dL
 - Absolute neutrophil count (ANC) $\geq 1.5 \times 10^9/L$ (≥ 1500 per mm 3)
 - Platelet count $\geq 100 \times 10^9/L$ ($\geq 100,000$ per mm 3)
 - Serum bilirubin $\leq 1.5 \times$ institutional upper limit of normal (ULN). This will not apply to subjects with confirmed Gilbert's syndrome (persistent or recurrent hyperbilirubinemia that is predominantly unconjugated in the absence of hemolysis or hepatic pathology), who will be allowed only in consultation with their physician.
 - AST (SGOT)/ALT (SGPT) $\leq 2.5 \times$ institutional upper limit of normal unless liver metastases are present, in which case it must be ≤ 5 x ULN
 - Serum creatinine CL >40 mL/min by the Cockcroft-Gault formula (Cockcroft and Gault 1976) or by 24-hour urine collection for determination of creatinine clearance.
12. Evidence of post-menopausal status OR negative urinary or serum pregnancy test for female pre-menopausal patients. Women will be considered post-menopausal if they have been amenorrheic for 12 months without an alternative medical cause. The following age-specific requirements apply:
 - Women <50 years of age would be considered post-menopausal if they have been amenorrheic for 12 months or more following cessation of exogenous hormonal treatments and if they have luteinizing hormone and follicle-stimulating hormone levels in the post-menopausal range for the institution or underwent surgical sterilization (bilateral oophorectomy, or hysterectomy).
 - Women ≥ 50 years of age would be considered post-menopausal if they have been amenorrheic for 12 months or more following cessation of all exogenous

hormonal treatments, had radiation-induced menopause with last menses >1 year ago, had chemotherapy-induced menopause with last menses >1 year ago, or underwent surgical sterilization (bilateral oophorectomy, bilateral salpingectomy or hysterectomy).

13. Female subjects of childbearing potential should have a negative urine or serum pregnancy within 72 hours prior to receiving the first dose of study medication. If the urine test is positive or cannot be confirmed as negative, a serum pregnancy test will be required.
14. Female subjects of childbearing potential should be willing to use 1 method of highly effective birth control or be surgically sterile, or abstain from heterosexual activity for the course of the study through 180 days after the last dose of study medication (Reference Section 8.1). Subjects of childbearing potential are those who have not been surgically sterilized or have not been free from menses for > 1 year.
15. Male subjects should agree to use an adequate method of contraception starting with the first dose of study therapy through 180 days after the last dose of study therapy.
16. Patient is \geq 5 years free of another primary malignancy, except: a) if the other malignancy is basal cell carcinoma or cervical carcinoma in situ or b) if the other primary malignancy is not considered clinically significant and is requiring no active intervention

4.5 Exclusion Criteria:

The subject **must be excluded** from participating in the trial if the subject:

1. Is currently participating in or has participated in a study of an investigational agent or using an investigational device within 4 weeks of the first dose of treatment.
2. Has a target lesion/s for SBRT that demonstrate any of the following:
 - a. located within 2 cm of the proximal bronchial tree
 - b. > 5 cm (> 50 cc) in greatest dimension
3. Has a target lesion/s in a region that previously received high dose RT (>50 Gy) demonstrating any of the following:
 - a. carotid artery encasement (> 180 degrees)

- b. unprotected carotid artery (i.e. skin is directly over the carotid without intervening soft tissue, especially after prior neck dissection without a vascularized free flap) (a&b due to risk of carotid blow out)
 - c. skin infiltration by tumor (due to risk of fistula)
 - d. located in the larynx/hypopharynx primaries (due airway threat)
 - e. treated with high dose radiation therapy (>50 Gy) within 6 months or less of trial enrollment
4. Prior receipt of an anti-PD-1, anti-PDL1 or anti-CTLA4 immune checkpoint inhibitor.
5. Current or prior use of immunosuppressive medication within 14 days before the first dose of nivolumab or ipilimumab. The following are exceptions to this criterion:
 - Intranasal, inhaled, topical steroids, or local steroid injections (e.g., intra articular injection)
 - Systemic corticosteroids at physiologic doses not to exceed 10 mg/day of prednisone or its equivalent
 - Steroids as premedication for hypersensitivity reactions (e.g., CT scan premedication)
6. Has received a prior monoclonal antibody within 4 weeks prior to study Day 1 or who has not recovered (i.e., \leq Grade 1 or at baseline) from adverse events due to agents administered more than 4 weeks earlier.
7. Has received prior chemotherapy, targeted small molecule therapy, or radiation therapy within 2 weeks prior to study Day 1 or who has not recovered (i.e., \leq Grade 1 or at baseline) from adverse events due to a previously administered agent.
 - Note: Subjects with \leq Grade 2 neuropathy are an exception to this criterion and may qualify for the study.
 - Note: If subject received major surgery, they must have recovered adequately from the toxicity and/or complications from the intervention prior to starting therapy.
8. Has a known additional malignancy that is progressing or requires active treatment. Exceptions include basal cell carcinoma of the skin, squamous cell

carcinoma of the skin, or in situ cervical cancer that has undergone potentially curative therapy.

9. Has known brain metastases or spinal cord compression unless the patient is stable (asymptomatic; no evidence of new or emerging brain metastases; and stable and off steroids for at least 14 days prior to start of study treatment). Following radiotherapy and/or surgery of the brain metastases patients must wait 4 weeks following the intervention and before initiating study treatment with imaging to confirm stability.
10. Has an active autoimmune disease requiring systemic treatment within the past 2 years or a documented history of clinically severe autoimmune disease, or a syndrome that requires systemic steroids or immunosuppressive agents. Subjects with vitiligo or resolved childhood asthma/atopy would be an exception to this rule. Subjects that require intermittent use of bronchodilators or local steroid injections would not be excluded from the study. Subjects with hypothyroidism stable on hormone replacement will not be excluded from the study.
11. Has a history of or evidence of active interstitial lung disease or non-infectious pneumonitis.
12. Has an active infection requiring systemic therapy.
13. Has a history or current evidence of any condition, therapy, or laboratory abnormality that might confound the results of the trial, interfere with the subject's participation for the full duration of the trial, or is not in the best interest of the subject to participate, in the opinion of the treating investigator.
14. Has known psychiatric or substance abuse disorders that would interfere with cooperation with the requirements of the trial.
15. Is pregnant or breastfeeding, or expecting to conceive or father children within the projected duration of the trial, starting with the pre-screening or screening visit through 180 days after the last dose of trial treatment.
16. Has a known history of Human Immunodeficiency Virus (HIV) (HIV 1/2 antibodies).

17. Has evidence of acute or chronic hepatitis B, or hepatitis C
18. Has received a live vaccine within 30 days prior to the first dose of trial treatment.
19. Has a history of primary immunodeficiency or an allogeneic organ transplant
20. Known history of previous clinical diagnosis of tuberculosis
21. Uncontrolled intercurrent illness including, but not limited to symptomatic congestive heart failure, uncontrolled hypertension, unstable angina pectoris, cardiac arrhythmia, active peptic ulcer disease or gastritis, seizures

5. TREATMENT

5.1 Systemic Therapy

5.1.1 Dosage and Administration

The treatment to be used in the run-in phase (initial 6 patients) of this trial is outlined in the table below. If ≤ 1 DLT is observed in the run-in phase, then the remaining 14 patients will be provided treatment per the following:

Drugs	Dose/Potency	Dose Frequency	Route of Administration	Regimen/Treatment Period
Weeks 1-24				
1. Nivolumab	3 mg/kg	Q2 weeks	IV infusion	Maximum of 12 doses
2. Ipilimumab	1mg/kg	Q6 weeks	IV infusion	Maximum of 4 doses
Weeks 25-52				
1. Nivolumab	480mg IV flat dose	Q4 weeks	IV infusion	Maximum of 8 doses

If 2 or more DLTs (defined in Section 5.1.2) are observed in the run-in phase, the following treatment will be used for the remaining 14 patients to be treated on the clinical trial protocol:

Drugs	Dose/Potency	Dose Frequency	Route of Administration	Regimen/Treatment Period
Weeks 1-24				
1. Nivolumab	3 mg/kg	Q4 weeks	IV infusion	Maximum of 6 doses
2. Ipilimumab	1mg/kg	Q8 weeks	IV infusion	Maximum of 3 doses
Weeks 25-52				
1. Nivolumab	480mg IV flat dose	Q6 weeks	IV infusion	Maximum of 4 doses

Patients who experience a DLT in the run-in phase, will have dose interruptions/reductions as outlined in Section 5.1.3.

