Study Design

This is a single arm, open label, prospective study evaluating the safety and clinical efficacy of the combination of nivolumab, ipilimumab and hypofractionated palliative radiation therapy (SBRT) in patients with advanced salivary gland cancer.

Patients enrolled will receive the following treatment (see Section 5.1.1):

1. Nivolumab 3mg/kg IV Q 2 weeks x 12 doses followed by Nivolumab 480 mg IV Q4 weeks x 8 doses
2. Ipilimumab 1 mg/kg IV Q6 weeks x 4 doses
3. Hypofractionated radiation therapy (SBRT) given to a total dose of 24Gy given in 3 fractions every other day over 1 week and initiated 2 weeks after the first dose of nivolumab and ipilimumab. The target lesion will be a local/regional or metastatic disease site that per the multidisciplinary head and neck team, requires local control for palliation and/or prevention of impending symptoms.

Both nivolumab and ipilimumab have well established toxicity profiles as a single agent and in combination. However, since the combination of nivolumab, ipilimumab and palliative radiation has not previously been described or studied, the first 6 patients who will be enrolled in this study will represent the initial safety run-in phase. Patients will receive full dose nivolumab and ipilimumab. Enrollment will be halted until these first 6 patients complete the first 12 weeks of treatment and acute toxicities will be reviewed. If more than 2 DLTs (to be defined in Section 5.1.2) are noted in this 6 patient cohort, a dose modification will be implemented (Section 5.1.1) for the remaining 14 patients who will be enrolled in the expansion cohort. Enrollment period is 24 months and duration of the trial 48 months.

Study Population

The study aims to enroll patients with salivary gland carcinomas (WHO, 2005), who are not candidates for curative intent therapy and who have a target lesion (either local/regional or distant metastatic site involving the lung and/or bone), that requires local control for palliation, as determined by a multidisciplinary team.

Inclusion Criteria:

1. Histologically proven salivary gland carcinoma (WHO, 2005) arising from a previous head and neck primary site, and located within the head and neck region, lung or bone, and who are not candidates for curative intent therapy.
2. ≥ 18 years old at the time of signing informed consent.

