4.2 Study Schema

Note: refer to Dosing and Administration (Section 5.1.1) for further details on treatment scenarios.

Clinical Study Protocol RG1718030
Drug Substance: Nivolumab and Ipilimumab
IND Number:140818
Protocol version 3.0 April 17, 2019

Both ipilimumab and nivolumab are FDA approved, and the safety profile of both agents have been extensively studied. However, because the combination with radiation has not been previously studied, the first 6 patients of this study will represent the initial run-in phase of the triplet combination of nivolumab, ipilimumab and palliative radiation. The initial doses of ipilimumab and nivolumab will be administered on day 1 of therapy.

Stereotactic radiation will be initiated on Week 3 of treatment. SBRT will be delivered to a total dose of 24 Gy, given in 3 fractions of 8Gy every other day. Treatment will be continued according to the study schema unless patient withdraws consent, has confirmed disease progression, and/or develops toxicity that results in treatment discontinuation.

Enrollment will be halted until these first 6 patients complete the first 12 weeks of treatment and acute toxicities will be reviewed. If more than 2 DLTs (to be defined in Section 5.1.2) are noted in this six patient cohort, a dose modification will be implemented (Section 5.1.1) for the remaining 14 patients who will be enrolled in the expansion cohort.

Serum correlative studies will be collected at the following timepoints: at baseline, prior to week 8, and prior to week 16 of treatment. Archived formalin fixed paraffin embedded tissue (obtained in the 12 months prior to trial enrollment) will be collected from patients enrolled. If the patient does not have archived tissue available, a fresh biopsy will be obtained. Tissue requirement will be waived if deemed contraindicated or not clinically available/accessible for resection per the treating physician (PI approval required).

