5.1.2 Definition of DLT

Dose-limiting toxicities (DLTs) will be evaluated during the run-in phase consisting of the first 6 patients enrolled in this trial. The period for evaluating DLTs will be from the time of first administration of nivolumab and ipilimumab until 12 weeks. Adverse event monitoring will continue for these subjects throughout the course of their treatment as outlined in the Schedule of Study Assessments, these adverse events will include potential XRT related toxicities. Subjects who do not remain on the study up to this time for reasons other than DLT will be replaced with another subject. Grading of DLTs will follow the guidelines provided in the Common Terminology Criteria for Adverse Events (CTCAE) version 5.0.

A DLT will be defined as any Grade 3 or higher toxicity that occurs during the DLT evaluation period. Toxicity that is clearly and directly related to the primary disease or to another etiology is excluded from this definition. The following will be DLTs:

- Any Grade 4 irAE
- Any \geq Grade 3 colitis
- Any Grade 3 or 4 noninfectious pneumonitis irrespective of duration

- Any Grade 2 pneumonitis that does not resolve to \leq Grade 1 within 3 days of the initiation of maximal supportive care
- Any Grade 3 irAE, excluding colitis or pneumonitis, that does not downgrade to Grade 2 within 3 days after onset of the event despite optimal medical management including systemic corticosteroids or does not downgrade to \leq Grade 1 or baseline within 14 days
- Liver transaminase elevation $> 8 \times$ ULN or total bilirubin $> 5 \times$ ULN
- Any \geq Grade 3 non-irAE, except for the exclusions listed below
 - Grade 3 fatigue lasting \leq 7 days
 - Grade 3 endocrine disorder (thyroid, pituitary, and/or adrenal insufficiency) that is managed with or without systemic corticosteroid therapy and/or hormone replacement therapy and the subject is asymptomatic
 - Grade 3 inflammatory reaction attributed to a local antitumor response (e.g., inflammatory reaction at sites of metastatic disease, lymph nodes, etc.)
 - Concurrent vitiligo or alopecia of any AE grade
 - Grade 3 infusion-related reaction (first occurrence and in the absence of steroid prophylaxis) that resolves within 6 hours with appropriate clinical management

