8.4 STUDY STOPPING RULE

In keeping with the study primary endpoint, a stopping rule will be implemented in the unlikely event that the combination under study is deemed to have unacceptably high toxicities. Enrollment will be halted if more than 3 patients experience a Grade 4 or higher drug related toxicity (CTCAE v. 5) during the trial treatment period or up to 30 days after the last investigational drug infusion. The likelihood of observing more than 3 Grade 4+ drug-related adverse events is 80% if the true

rate is 20% and the likelihood is 91% if the true rate is 25%. This rule has an 83% chance of prematurely discontinuing trial enrollment after the 1st 10 patients are enrolled if the true rate of Grade 4 drug related toxicity is 40%. The study will be reviewed by the University of Washington/Fred Hutch Cancer Consortium Data and Safety Monitoring Committee (DSMC

STATISTICAL CONSIDERATIONS

All patients enrolled in the study, including those in the run-in phase will be included in the analysis of toxicity and efficacy.

Safety and tolerability is the primary endpoint of this study, and all patients enrolled will be assessed for this endpoint. Adverse events will be recorded and graded based on CTCAE v. 5, and their relationship to the experimental agents reported.

Similarly, all patients enrolled in the study (i.e., the initial 6 patient cohort, and the additional 14 patient expansion) will be included in the efficacy analyses. Clinical responses to the combination of nivolumab, ipilimumab and hypofractionated radiation will be based on RECIST 1.1 criteria. Oncologic outcome endpoints such as progression free and overall survival will be calculated from the date of study enrollment, until disease progression or death from any cause, respectively. Survival estimates will be calculated using the Kaplan-Meier method.

Exploratory endpoints of this study include correlative work performed on research serum and tissue samples.

Sample size determination

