9. STUDY MANAGEMENT

All investigators on the protocol will receive formal training in the ethical conduct of human research. Institutional support of trial monitoring is provided in accordance with the Cancer Consortium's data and safety monitoring plan

Monitoring of the study

Institutional support of trial monitoring will be in accordance with the Fred Hutch/University of Washington Cancer Consortium Institutional Data and Safety Monitoring Plan. Under the provisions of this plan, Fred Hutch Clinical Research Support coordinates data and compliance monitoring conducted by consultants, contract research organizations, or Fred Hutch employees unaffiliated with the conduct of the study. Independent monitoring visits occur at specified intervals determined by the assessed risk level of the study and the findings of previous visits per the institutional DSMP.

In addition, protocols are reviewed as needed by the Consortium Data and Safety Monitoring Committee (DSMC), Fred Hutch Scientific Review Committee (SRC) and the Fred Hutch/University of Washington Cancer Consortium Institutional Review Board (IRB). The review committees evaluate accrual, adverse events, stopping rules, and adherence to the applicable data and safety monitoring plan for studies actively enrolling or treating patients. The IRB reviews the study progress and safety information to assess continued acceptability of the risk-benefit ratio for human subjects. Approval of committees as applicable is necessary to continue the study. The trial will comply with the standard guidelines set forth by these regulatory committees and other institutional, state, and federal guidelines.

Data Management

The Protocol Director, or her designees, will prepare and maintain adequate and accurate participant case histories with observations and other data pertinent to the study. Original source documents should be transcribed to Case Report Forms (CRFs) and used to analyze the study data. Source documents include hospital records, clinical charts, laboratory and pharmacy records, and recorded electronic data.

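### The run-in decision rule contradicts itself at exactly 2 DLTs, and no DLT count keeps enrolment closed

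*Combined protocol and SAP*

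**What the plan says.** Section 4.2, like the synopsis, provides a pause: "Enrollment will be halted until these first 6 patients complete the first 12 weeks of treatment and acute toxicities will be reviewed". DLTs are Grade 3 or higher toxicities with listed exceptions, plus unresolved Grade 2 pneumonitis. Section 5.1.2 sets the window: "The period for evaluating DLTs will be from the time of first administration of nivolumab and ipilimumab until 12 weeks". It limits DLT evaluation to the first six patients.

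The consequence of the count is stated in three places.

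- Synopsis, Study Design: "If more than 2 DLTs (to be defined in Section 5.1.2) are noted in this 6 patient cohort", the dose is modified.
- Section 4.2: the same trigger, after which "a dose modification will be implemented (Section 5.1.1) for the remaining 14 patients who will be enrolled in the expansion cohort".
- Section 5.1.1: at most 1 DLT keeps the original schedule for the remaining 14. Otherwise, "If 2 or more DLTs (defined in Section 5.1.2) are observed in the run-in phase, the following treatment will be used".

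The alternative schedule keeps nivolumab at 3 mg/kg and ipilimumab at 1 mg/kg but spaces them out: nivolumab every 4 weeks instead of 2, ipilimumab every 8 instead of 6, then flat-dose nivolumab every 6 weeks instead of 4. It does not alter SBRT.

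The numeric halt is in section 8.4: "Enrollment will be halted if more than 3 patients experience a Grade 4 or higher drug related toxicity". Section 8.4 also names the "Cancer Consortium Data and Safety Monitoring Committee (DSMC" as reviewing the study; that sentence is cut off in the text available. Section 3 has the Protocol Director and staff review adverse events weekly. Section 9 describes committee oversight and adds: "Approval of committees as applicable is necessary to continue the study".

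**The concern.** The run-in exists because the drug pair had not been studied with radiation. Two things could go wrong when its result is read.

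First, with 2 DLTs the site would find an instruction to reduce in one section and a trigger not yet met in two others. Nothing says which section governs, or whether DLTs are counted as events or as patients.

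Second, reducing the frequency is a reasonable answer to 2 or 3 affected patients. It is a weaker answer to 5 or 6, because the mg/kg doses and SBRT stay the same and the new schedule has no DLT evaluation of its own. At such counts one would expect a written criterion for staying closed, and none is tied to the DLT count.

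**Working it through.** **Threshold conflict.** Set side by side, with the count as number of DLTs:

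| DLTs | 5.1.1 | 4.2 and synopsis |
|---|---|---|
| 0 or 1 | original schedule | modification not triggered |
| 2 | reduced schedule | modification not triggered |
| 3 or more | reduced schedule | modification triggered |

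The protocol gives no DLT rate, so p is an assumption. Counting patients, P(X = 2) = 15 p²(1 − p)⁴:

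- p = 0.2: 15 × 0.04 × 0.4096 = 0.246
- p = 0.3: 15 × 0.09 × 0.2401 = 0.324
- p = 0.4: 15 × 0.16 × 0.1296 = 0.311

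**What the reduced schedule changes in the DLT window.** Nominal infusion days within days 1–84:

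- Nivolumab every 2 weeks: days 1, 15, 29, 43, 57, 71 (6). Every 4 weeks: days 1, 29, 57 (3).
- Ipilimumab every 6 weeks: days 1, 43 (2). Every 8 weeks: days 1, 57 (2).

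Nivolumab infusions are halved. Ipilimumab stays at 2, with the second moved from week 7 to week 9.

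**Section 8.4: its own figures first.** The plan states 80% and 91% at true rates of 20% and 25%, and 83% after 10 patients at 40%. Exact binomial tails, taking n = 20 for the first two:

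| n, true rate | Stated | 4 or more (as worded) | 3 or more |
|---|---|---|---|
| 20, 20% | 80% | 58.9% | 79.4% |
| 20, 25% | 91% | 77.5% | 90.9% |
| 10, 40% | 83% | 61.8% | 83.3% |

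The stated figures fit 3 or more, not more than 3, so both readings are carried forward.

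**Does 8.4 cover a failed run-in?** Suppose 4 or more of 6 patients have a DLT, at an assumed DLT rate p, and a share s of DLT patients have a Grade 4 or higher drug-related event (also assumed). The chance that 8.4 is also crossed among those patients is

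Σ P(X = x) × P(Bin(x, s) ≥ r) ÷ P(X ≥ 4), summed over x = 4, 5, 6, with r = 4 or 3.

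For p = 0.5, s = 0.5, r = 4: (0.2344 × 0.0625 + 0.0938 × 0.1875 + 0.0156 × 0.3438) ÷ 0.3438 = 0.109. With r = 3: (0.2344 × 0.3125 + 0.0938 × 0.5 + 0.0156 × 0.6562) ÷ 0.3438 = 0.379.

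| Share s | Reading of 8.4 | p = 0.5 | p = 0.6 | p = 0.7 |
|---|---|---|---|---|
| half | as worded | 11% | 13% | 16% |
| half | 3 or more | 38% | 41% | 44% |
| quarter | as worded | 0.9% | 1.1% | 1.4% |
| quarter | 3 or more | 7% | 8% | 9% |

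These ignore Grade 4 or higher drug-related events that are not DLTs, such as lymphopenia, and so somewhat understate 8.4.

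**Proposed hold.** Binomial, n = 6:

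| True DLT rate | 20% | 30% | 40% | 50% | 60% | 70% |
|---|---|---|---|---|---|---|
| P(4 or more) | 2% | 7% | 18% | 34% | 54% | 74% |
| P(5 or more) | 0.2% | 1% | 4% | 11% | 23% | 42% |

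**The case against.** A reader might infer that nothing can stop this trial after a bad run-in, that 14 more patients must be enrolled whatever happens, or that nobody reviews the run-in data. The documents support none of these.

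- Twenty patients is a stated maximum, and 5.1.1 is a dosing section. It says which schedule applies to later patients and creates no duty to enrol them.
- Enrolment does pause for a toxicity review. Section 3 assigns weekly adverse event review to the Protocol Director and staff, and section 9 makes committee approval, as applicable, a condition of continuing. What the cut-off DSMC sentence in 8.4 went on to say cannot be known.
- Section 8.4 runs over all 20 patients and may act later. At DLT rates of 50%, 60% and 70%, as worded, it is crossed by 20 patients with probability 77%, 89% and 96% (half share) or 23%, 35% and 47% (quarter share), if the reduced schedule does not lower the rates. These are tails of Bin(20, p × s) at 4 or more.

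It can also be said that a failed run-in is unlikely. The sample size section plans around 28% serious treatment-related events and 30% Grade 3 or higher drug-related toxicity. If the DLT rate were 20% to 30%, 4 or more of 6 would occur 2% to 7% of the time. The 50% to 70% rates and the half and quarter shares have no source in the protocol.

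All of that stands, and it makes the missing ceiling a gap in the written rule, not an absence of protection. It does not answer two things: the conflict at 2 DLTs, which arises at quite ordinary DLT rates, and the fact that 8.4 would not count six of six patients with Grade 3 DLTs.

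**Conclusion.** The point holds in two parts.

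The threshold conflict is wrong as written and needs no assumption to establish. Its chance of mattering, 25% to 32%, assumes true DLT rates of 20% to 40%, independent patients and counting by patient.

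The missing ceiling is a design weakness. No DLT count keeps enrolment closed, and the only response named from 2 to 6 of 6 is a less frequent schedule without its own DLT evaluation. Section 8.4 narrows the gap but does not close it. After 4 or more DLT patients at assumed rates of 50% to 70%, it is also crossed among them 11–16% of the time as worded, or 38–44% read as 3 or more, if half have Grade 4 or higher drug-related events. If a quarter do, the figures are about 1% and 7–9%. Otherwise, staying closed rests on judgment, for which the available text gives no DLT criterion.

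Both parts should be amended.

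**What to change.** 1. Use one threshold throughout, counted in patients: 2 or more of 6 evaluable run-in patients with at least one DLT leads to the reduced schedule. This replaces the more-than-2 wording in 4.2 and the synopsis. The 5.1.1 threshold is the better one to keep because its two branches already cover every count.
2. Add to 5.1.1, 4.2 and the synopsis: if 4 or more of the 6 evaluable run-in patients have a DLT, enrolment stays halted until the DSMC has reviewed the data and agreed in writing to reopen. A cut-off of 5 is an acceptable alternative.

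The cost is a short amendment, which section 3 requires the IRB to approve, and an occasional extra DSMC pause: 2%, 7% and 18% at true DLT rates of 20%, 30% and 40%, or 0.2%, 1% and 4% with a cut-off of 5. The hold guards against a clearly failed run-in. At a true rate of 50% it acts only 34% of the time (11% with a cut-off of 5), so it should not be presented as a sensitive test at that rate.
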